8.10. Concomitant medication

Details of all concomitant medications will be recorded on the trial eCRF on a concomitant medications log. Where possible participant's regular treatments received for the management of bronchiectasis should remain stable throughout the trial period.

8.11. Trial restrictions

	Treatment	Trial restrictions
All arms		To avoid contamination between the arms, participants who develop an exacerbation during the study and require antibiotic treatment should receive an antibiotic other than doxycycline. If participants are not able to safely avoid doxycycline during the trial period they should not be enrolled in the study.
Arm 2	Disulfiram	Alcohol Participants will be required to consent to not consuming alcohol for duration of treatment and at least 14 days after stopping treatment. Written advice will be provided to participants about how to avoid products containing alcohol during the trial period.
Arm 3	Dipyridamole	Participants should not commence new oral anticoagulant drugs during the trial period. Participants needing to initiate anticoagulants should withdraw from the study.
Arm 4:	Doxycycline	No restrictions. Exacerbations of bronchiectasis should be treated with an alternative antibiotic.
All	Nasal brushing	Participants should not have a nasal brushing performed if they are receiving anticoagulants (oral anticoagulants or warfarin) or have a history of deviated nasal septum, base of skull fracture or severe epistaxis. If any of these are present the nasal brushing will be omitted. This will not affect their participation in the trial.

WOCBP must be willing to have pregnancy testing prior to trial entry and at each research visit, unless the participant has been randomised to usual care.

A woman is considered of childbearing potential, i.e. fertile, following menarche and until becoming post-menopausal unless permanently sterile. A post-menopausal state is defined as no menses for 12 months without an alternative medical cause (including use of hormone replacement therapy).

In addition, WOCBP must be willing to use a form of a medically approved birth control method throughout the trial (and for minimum of 4 weeks after last dose), unless randomised to usual care, which include:

- combined (estrogen and progestogen containing) hormonal contraception associated with inhibition of ovulation:
 - oral
 - intravaginal
 - transdermal
- progestogen-only hormonal contraception associated with inhibition of ovulation:
 - oral
 - injectable
 - implantable
- intrauterine device (IUD)
- intrauterine hormone-releasing system (IUS)

- bilateral tubal occlusion
- vasectomised partner
- sexual abstinence, when this is in line with the preferred and usual lifestyle of the participant, abstinence is acceptable only as true abstinence. Periodic abstinence (e.g., calendar, ovulation, symptom-thermal, post-ovulation methods) and withdrawal are not acceptable methods of contraception.

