7.3. Randomisation scheme

Participants will be randomised equally to any open arms they are eligible for. Participants will be allocated to an arm using a minimisation algorithm, with factors for centre, *Pseudomonas aeruginosa* infection recorded in the last 2 years and long-term use of macrolides.

Randomisation will initially open with a control arm and 3 treatment arms. When a treatment arm has recruited to its target, randomisation to that arm will be closed. When a new treatment arm is added, randomisation to that arm will be opened for all participants meeting the eligibility criteria for that arm.

Participants who have completed 56 days of follow-up (end of trial) may be rescreened and re-randomized if they are willing to participate in the trial again. Participants will receive a new copy of the current PIS, will be asked to complete a new Informed Consent Form, be given a new, unique participant identification number and eligibility will be rechecked prior to randomisation. All trial activities will be carried out as per protocol. Re-randomisation will be performed in the same way as for initial randomisations. Patients can be randomised a maximum of three times (i.e. initial randomisation and two re-randomisations).

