7.10. Withdrawal criteria

Participants are free to withdraw at any time and are not obliged to give reason(s). The CI, PI or delegate will make a reasonable effort to ascertain the reason(s), both for those who express their right to withdraw and for those lost to follow up, while fully respecting the individual's rights.

The investigator may withdraw a patient at any time if it is in the best interest of the patient and treatment continuation would be detrimental to the patient's well-being. A full explanation will be provided. If the trial is being conducted on an intention to treat basis, and the participant has been randomised and given one or more doses of IMP, s/he will be asked to complete trial visits as per the protocol, if the CI considers it appropriate. This would allow

for an intention to treat analysis - but will be censored in the per-protocol analysis. Participants are free to refuse to do so. Withdrawn participants will not be prescribed IMP.

Those withdrawn, including those lost to follow-up, will be identified and a descriptive analysis of them provided, including the reasons for their loss, if known, and its relationship to treatment and outcome.

7.11. If a participant withdraws or is withdrawn, they have the right to ask for their data and samples held to be removed/disposed of, changed or deleted. This might not always be possible if it means the data/samples cannot be used to do the research, if this is the case, participants will be informed. Storage and analysis of clinical samples

The collection, processing and storage of samples will be detailed in the Laboratory Manual. The analysis of samples will be detailed in the Laboratory Analytical Plan.

Blood and sputum samples will be obtained as per Laboratory Manual. Processing of blood for serum generation and cell isolation will be completed at sites, details of how processing will be carried out will be included in the Laboratory Manual. The resulting serum, sputum supernatant, whole sputum and cells will be stored at site.

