8.7. Dosage schedules, open treatment arms

	Treatment	Dosage schedule	Duration
Arm 2	Disulfiram	Two 200mg tablets once daily	28 days
Arm 3	Dipyridamole	One 200mg capsule twice daily	28 days
Arm 4	Doxycycline	One 100mg capsule once daily	28 days

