10.3. Statistical analysis plan

The primary analysis will be performed on an intention-to-treat basis. Analysis of covariance (ANCOVA) will be used to compare the log₁₀-transformed NE between the control and each treatment arm after 28 days, with baseline log₁₀-transformed NE included as a covariate in addition to terms for trial arm, minimisation factors and relevant baseline prognostic variables. Missing data will be dealt with using multiple imputation, assuming missing-at-random is an appropriate assumption; methods exploring other mechanisms may be performed as appropriate. The estimated difference between the arms in log₁₀-transformed NE will be presented along with the corresponding 80% confidence interval and 1-sided p-value. Analysis makes a working independence assumption. To account for the re-randomisation of patients, cluster-robust standard errors will be computed (Kahan et al. 2021)

NE over the entire study period will be compared between arms using linear mixed effects models, including fixed effect terms for trial arm, stratification factors and relevant baseline prognostic variables, and a random intercept participant effect. Quality of life outcomes will be compared between arms using a similar approach.

Analysis of time to first exacerbation will be conducted using a Cox regression model incorporating trial arm, stratification factors and relevant baseline prognostic variables. The hazard ratio, 80% CI and 1-sided p-value associated with study arm will be obtained from this model, using cluster-robust standard errors. A Kaplan-Meier plot will be used to illustrate the relative time to first exacerbation in each arm and contemporaneous controls, with proportion of patients exacerbation-free after 28 and 56 days and associated 80% CIs provided.

Safety will be assessed by tabulating AEs that occurred in at least 10% of the safety population participants in either arm; these will be further broken down by severity. Treatment compliance (including number of expected doses taken/missed, number of dose

reductions (if applicable), reasons for missed doses/dose reductions, etc) will be summarised for each treatment arm.

Full details, including planned sensitivity analyses and the approach for handling missing data, will be provided in a separate Statistical Analysis Plan.

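### In the dipyridamole arm only, section 8.11 turns starting an anticoagulant into withdrawal from the study, so follow-up after that event is discretionary in Arm 3 and routine in usual care

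*Protocol*

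**What the plan says.** The table in Protocol section 8.11 has two sentences in the dipyridamole row: "Participants should not commence new oral anticoagulant drugs during the trial period" and "Participants needing to initiate anticoagulants should withdraw from the study". The usual care, disulfiram and doxycycline arms have no such rule. The only other mention of anticoagulants in the table concerns nasal brushing, which is omitted for people taking them without affecting their participation.

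Dipyridamole is given for 28 days (section 8.7). The trial period is not formally defined, but section 7.3 treats day 56 as a participant's end of trial: "Participants who have completed 56 days of follow-up (end of trial) may be rescreened". The disulfiram row, by contrast, ties its restriction to treatment: "not consuming alcohol for duration of treatment and at least 14 days after stopping treatment".

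Section 7.10 describes what follows withdrawal. Where the trial is on an intention-to-treat basis and at least one dose has been given, "s/he will be asked to complete trial visits as per the protocol, if the CI considers it appropriate". The participant may refuse. It adds: "Withdrawn participants will not be prescribed IMP". Section 10.3 states: "The primary analysis will be performed on an intention-to-treat basis", with multiple imputation for missing data under a missing-at-random assumption.

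**The concern.** The trigger is a post-randomisation event and the stated consequence is leaving the study. Stopping a drug and stopping follow-up are different decisions, and 8.11 merges them in one arm. After day 28 there is no trial drug left to stop, so the rule can then only end follow-up.

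A usual-care participant who starts an anticoagulant is followed to day 56 as a matter of routine. A dipyridamole participant with the same event is followed only if the CI thinks it appropriate, and the CI is not blinded to arm. An intention-to-treat comparison should not rest on a follow-up rule that differs by arm. The safety record is the more practical worry. Appendix 1 names bleeding as a dipyridamole risk that rises with anticoagulation, and adverse events are recorded only to the last trial visit (section 9.3). Recording could therefore stop in Arm 3 just when an anticoagulant has been started.

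The two sentences also differ in scope: one refers to oral anticoagulants, the other to anticoagulants without qualification.

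**Working it through.** **1. Period covered.** End of follow-up is day 56 (section 7.3) and end of dipyridamole is day 28 (section 8.7). 56 − 28 = 28 days of the restricted period are off drug, if the trial period means day 56.

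**2. Sections side by side.**
- 8.11: an Arm 3 participant needing an anticoagulant leaves the study.
- 7.10: a withdrawn participant who has taken a dose stops trial drug and is asked to attend visits, at the CI's discretion.
- 10.3: all participants are analysed as randomised.

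Sections 7.10 and 10.3 fit together if follow-up continues. Section 8.11 does not say that it does.

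**3. Likely number.** The documents give no rate of starting anticoagulants, so annual rates r of 1% to 10% are assumed. Expected starts among 42 participants over d days = 42 × (1 − exp(−r × d/365.25)).

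| Assumed annual rate | By day 28 | By day 56 | Chance of at least one by day 56 |
|---|---|---|---|
| 1% | 0.03 | 0.06 | 6% |
| 2% | 0.06 | 0.13 | 12% |
| 5% | 0.16 | 0.32 | 28% |
| 10% | 0.32 | 0.64 | 48% |

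A broader assumption, that 2% to 5% start one within 56 days (for example by counting injectable use during admissions), gives 42 × 0.02 = 0.8 to 42 × 0.05 = 2.1.

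**4. The plan's power figure.** Inputs from section 10.1: difference 0.25 log10, SD 0.5, R² 0.1, up to 4 covariates, one-sided 10%, 42 per arm with up to 10% dropout. Residual SD = 0.5 × √0.9 = 0.474. Evaluable per arm = 42 × 0.9 = 37.8, taken as 37. The noncentral t with 37 + 37 − 6 = 68 degrees of freedom gives 83.4%, against 81.8% in Table 10.1.1. Using 35 per arm reproduces all four table values, so the table is slightly conservative.

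**5. Effect on power.** Losing 1, 2 or 3 more Arm 3 participants (36, 35 or 34 against 37) gives 83.0%, 82.6% or 82.2%.

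**6. Effect on the day-28 comparison.** Suppose k Arm 3 participants are lost before day 28, usual care keeps k similar ones, and these have log10 NE higher by δ (assumed; the documents give no such difference). Bias = k × δ/37.
- k = 1, δ = 0.25: 0.25/37 = 0.007, or 3% of the 0.25 target; one-sided type I error about 11%.
- k = 2, δ = 0.5: 1.0/37 = 0.027, or 11%; about 15%.
- k = 3, δ = 0.5: 1.5/37 = 0.041, or 16%; about 18%.

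Expected losses by day 28 in step 3 are below one, so the realistic effect is at or under the first line.

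**7. Which outcomes the off-drug days can touch.** By section 3.1, primary NE is at day 28 and time to first exacerbation covers days 0 to 28; neither can be changed by withdrawal after day 28. Open to loss are day-56 NE, QOL-B and BIM, exacerbation frequency to day 56, adverse events to day 56, and the day-56 exacerbation-free proportion that section 10.3 asks for.

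**The case against.** The strongest reply is that section 7.10 already handles this. It asks dosed participants to keep attending, says why, and describes withdrawal mainly as an end to prescribing. On that reading 8.11 means little more than stopping the drug. Much of this stands, and it rules out saying that Arm 3 necessarily loses these participants. What remains is that continued visits depend on the CI's judgement, and that for days 29 to 56 the reading leaves 8.11 with nothing to do.

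A reader might infer that the rule removes sicker participants and makes dipyridamole look better on exacerbations and serious adverse events. The documents do not support this. No section links needing an anticoagulant with NE, exacerbation or bronchiectasis severity. The triggering illness comes before withdrawal and would normally be on record already: serious adverse events are reported within 24 hours (section 9.3), hospitalisations for worsening bronchiectasis count as such (section 9.2), and data collected up to withdrawal are kept (section 7.2.1), subject to the removal request in section 7.10. Only later events are at risk.

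An arm-specific rule also has a documented basis, since sections 6.3.2, 8.9 and Appendix 1 all address bleeding risk with dipyridamole and anticoagulants. That can explain a rule about trial drug; it does not explain ending follow-up. The second sentence of the row may simply refer back to oral agents, but the text should say so. Finally, section 10.3 allows methods for other missing-data mechanisms, which helps but cannot replace data that could have been collected.

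**Conclusion.** The point holds in a limited form. Section 8.11 attaches study withdrawal to a post-randomisation event in one arm, by its natural reading for 28 days beyond treatment, and section 7.10 makes later follow-up discretionary where usual care has it as routine. This sits badly with the intention-to-treat analysis, though it falls short of an outright contradiction.

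The size is small: probably fewer than one to two of 42 participants, on assumed rates. Losing one lowers power from 83.4% to 83.0%, within the plan's 10% dropout allowance. Bias in day-28 NE is likely to be 3% of the target difference or less, and its direction is unknown. The main exposure is in day-56 outcomes and in adverse events after the anticoagulant starts. The conclusion rests on reading the trial period as ending at day 56. It is worth acting on because the correction is nearly free, not because the numbers are large.

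**What to change.** In section 8.11, separate trial drug from study participation. State that starting an anticoagulant does not in itself end participation; that scheduled visits, samples, and exacerbation and adverse event recording continue to day 56 as in usual care unless the participant declines; and that the start, with its date, is recorded as an intercurrent event. The existing nasal-brushing omission stays. Cross-refer to section 7.10 so that follow-up after this event does not depend on the CI's discretion, and check that both agree with section 10.3.

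The sponsor should also reconcile the oral and the unqualified anticoagulant wording, and say whether the rule differs between on-drug and post-drug days. What happens to trial drug is for the sponsor to state; no clinical rule is proposed here.

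The cost is about two sentences in 8.11 and a cross-reference. No visit is added beyond those in Appendix 4.

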8.12. Assessment of compliance with treatment

Adherence to trial drug will be checked by tablet counting at the last visit. Participants will also be asked at each visit regarding their adherence to taking the trial drug daily.

8.13. Name and description of each Non-Investigational Medicinal Product

Nil

9. PHARMACOVIGILANCE

9.1. Definitions

Term	Definition
Adverse Event (AE)	Any untoward medical occurrence in a participant to whom a medicinal product has been administered, including occurrences which are not necessarily caused by or related to that product.
Adverse Reaction (AR)	
An untoward and unintended response in a participant to an IMP which is related to any dose administered to that participant.
 
The phrase "response to an IMP" means that a causal relationship between a trial medication and an AE is at least a reasonable possibility, i.e. the relationship cannot be ruled out.
 
All cases judged by either the reporting medically qualified professional or the Sponsor as having a reasonable suspected causal relationship to the trial medication qualify as ARs. It is important to note that this is entirely separate to the known side effects listed in the SmPC. It is specifically a temporal relationship between taking the drug, the half-life, and the time of the event or any valid alternative etiology that would explain the event.

Serious Adverse Event (SAE)	
A SAE is any untoward medical occurrence that:
 
 • results in death • is life-threatening • requires inpatient hospitalisation or prolongation of existing hospitalisation • results in persistent or significant disability/incapacity • consists of a congenital anomaly or birth defect 
Other 'important medical events' may also be considered serious if they jeopardise the participant or require an intervention to prevent one of the above consequences.
 
NOTE: The term "life-threatening" in the definition of "serious" refers to an event in which the participant was at risk of death at the time of the event; it does not refer to an event which hypothetically might have caused death if it were more severe.

Serious Adverse Reaction (SAR)	An AE that is both serious and, in the opinion of the reporting Investigator, believed with reasonable probability to be due to one of the trial treatments, based on the information provided.

9.2. Operational definitions for (S)AEs

Worsening of bronchiectasis or bronchiectasis exacerbations during the trial will not be classed as an AE but is defined as an outcome. However, hospitalisations resulting from worsening of bronchiectasis will be recorded as AEs and reported as SAEs.

An abnormal laboratory finding, that requires medical intervention by the investigator, or a finding judged by the investigator as medically significant, will be reported as an AE. If clinical sequelae are associated with a laboratory abnormality, the diagnosis or medical condition will be reported (e.g. renal failure, haematuria) not the laboratory abnormality. Abnormal laboratory values that are not, in the investigator's opinion, medically significant and do not require intervention will not be reported as AEs.

A non-clinically significant, in the opinion of the investigator, worsening of a pre-existing condition during the trial will not be classed as an AE. Pre-specified elective hospitalisations for treatment planned prior to randomisation will not be considered as an AE. However, any AEs occurring during such hospitalisations will be recorded.

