1. BACKGROUND

Non-cystic bronchiectasis (hereafter referred to as bronchiectasis) is a chronic inflammatory disease with permanent bronchi dilatation, characterised by disabling productive cough, shortness of breath, and occasional haemoptysis (Barker 2002). Bronchiectasis is a heterogeneous condition that can either be a suppurative pulmonary disease on its own or overlap with other pulmonary diseases including asthma and chronic obstructive pulmonary disease ([name] et al. 2018). Data from the European Multicentre Bronchiectasis Audit and Research Collaboration (EMBARC) registry shows that approximately half of the patients with bronchiectasis experience two or more exacerbations a year, a major adverse event within the natural history of this disease. Patients who frequently exacerbate have double the mortality rate than patients who do not ([name] et al. 2014). Therefore, reducing exacerbations has now been an area of focus for most bronchiectasis research involving therapeutics.

There are few novel therapies in development for the treatment of bronchiectasis due to a lack of validated targets, and due to a lack of therapies with proof of concept to support further clinical development. The dominant mechanism of disease in bronchiectasis is chronic neutrophilic inflammation, which is near universal in patients with this condition, and which has been linked to disease severity, future exacerbations, and lung function decline. Excessive neutrophilic inflammation through the formation of neutrophil extracellular traps (NETs) is therefore a key therapeutic target in bronchiectasis ([name] et al. 2017). Dipeptidyl peptidase-1 inhibitors, which directly target neutrophilic inflammation, were recently shown to prolong time to first exacerbation in a phase 2 trial in bronchiectasis ([name] et al. 2020). Exacerbation reduction was predicted by a reduction in neutrophil elastase (NE) activity in sputum ([name] et al. 2020). NE has been shown to be a valid biomarker across multiple studies in bronchiectasis ([name] et al. 2017).

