3. OBJECTIVES AND OUTCOME MEASURES/ENDPOINTS

3.1. Table of endpoints/outcomes

Primary Objective		
Objective	Outcome Measures	Timepoint(s)
To evaluate the effect of a range of interventions compared to usual care on the activity of NE in sputum	Activity of sputum NE	Day 0 and 28
Secondary Objectives		
Objective	Outcome Measures	Timepoint(s)
To evaluate the effect of a range of interventions compared to usual care on the activity of NE in sputum	Activity of sputum NE	Days 0, 7, 14 and 56
To evaluate the effect of a range of interventions compared to usual care on time to onset of first bronchiectasis exacerbation	Time to first pulmonary exacerbation (EMBARC definition)	Days 0 to 28
To evaluate the effect of a range of interventions compared to usual care on quality of life	Quality of life-bronchiectasis (QOL-B) respiratory symptom scale, Bronchiectasis Impact Measure (BIM) questionnaire	Days 0, 7, 14, 28 and 56
To evaluate the effect of a range of interventions compared to usual care on clinical benefits	Bronchiectasis exacerbation and symptom tool (BEST) diary	Days 0 to 28
To evaluate the effect of a range of interventions compared to usual care on walking distance	Distance covered during 6-minute walk	Day 0, 28
To evaluate the safety of a range of interventions compared with usual care	Frequency of adverse events (AEs) and serious adverse events (SAEs)	Days 0 to 56
To evaluate the effect of a range of interventions on peripheral blood neutrophil function	Phagocytosis of bacteria Reactive oxygen species generation Degranulation Ex-vivo formation of neutrophil extracellular traps Mass cytometry (endpoints may vary depending on the experimental arm)	Day 0 to 28
Tertiary Objectives		
Objective	Outcome Measures	Timepoint(s)

To evaluate the effect of a range of interventions compared to usual care on bronchiectasis exacerbations	Frequency of pulmonary exacerbations (EMBARC definition)	Days 0 to 28; Days 0 to 56
To develop and validate additional biomarkers in sputum that are linked with clinical outcomes of bronchiectasis	Measure the concentration of MMPs and NETs in sputum, as well as other biomarkers e.g proteomics, bacterial load, microbiome	Days 0, 7, 14,28 and 56
To develop and validate additional biomarkers in blood that are linked with clinical outcomes of bronchiectasis	Measure serum biomarkers of inflammation and redox status	Days 0, 7, 14, 28 and 56

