Headache	
Headaches are a well-known transient side effects of dipyridamole, due to its vasodilatory properties. This often leads to discontinuation, as seen in 8% of patients who were enrolled into the dipyridamole arm in the Second European Stroke Prevention (ESPS2) Trial.
 
A bioequivalence trial comparing two different formulations of dipyridamole involving mostly young healthy adults found that 72% of volunteers reported at least one episode of headache over the course of two weeks. This bioequivalence trial also found that the volunteers are more likely to experience headache in the first week, 2-3 hours after the morning dose, and all volunteers recovered fully from the headaches regardless of severity. (Theis, Deichsel, and Marshall 1999)
	- Participants should be informed that they may experience transient headaches while initiating dipyridamole, and reassurance that it will improve with time.
Bleeding	
As an antiplatelet, patients may be at a higher risk of bleeding complications. Adding dipyridamole to anticoagulation increases the risk of bleeding by about 50% (Massel and Little 2013).
 
However, for patients not on anticoagulation, this risk was not seen in the large clinical trials performed in patients who had a Stroke or Transient Ischaemic Attack (TIA). In
	
- Participants who are on dual antiplatelet, any anticoagulant, or any coagulopathy should not be randomised to dipyridamole. Participants who are already on Aspirin are safe to be recruited.
 
- Participants who recently had any gastrointestinal bleeding, head trauma, or major operation within 30 days should not be randomised to dipyridamole

	ESPS2, patients who were randomised to placebo (n=1649) and dipyridamole alone (n=1654) reported similar events for bleeding any site, 74 and 77 respectively. ESPS2 also found that the bleeding risk between Aspirin (n=1649) and Aspirin plus Dipyridamole (n=1650) are similar at 135 and 144 events respectively (Diener et al. 1996).	

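### Section 9.2 lets haemoptysis that does not lead to hospitalisation be treated as disease worsening and left off the AE log, although bleeding is a named risk of dipyridamole

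*Protocol*

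**What the plan says.** Section 9.2 sets the exclusion: "Worsening of bronchiectasis or bronchiectasis exacerbations during the trial will not be classed as an AE but is defined as an outcome". It then makes one exception: "However, hospitalisations resulting from worsening of bronchiectasis will be recorded as AEs and reported as SAEs". It makes no exception for bleeding and does not mention haemoptysis.

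The only mention of haemoptysis in the protocol is in the Background, where bronchiectasis is "characterised by disabling productive cough, shortness of breath, and occasional haemoptysis".

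Appendix 1, under dipyridamole, says: "As an antiplatelet, patients may be at a higher risk of bleeding complications". For patients not on anticoagulation it cites a stroke-prevention trial in which placebo and dipyridamole groups "reported similar events for bleeding any site, 74 and 77 respectively".

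Section 3.1 lists two exacerbation outcomes, time to first and frequency, both by the EMBARC definition. It also lists QoL-B and BIM (to day 56), the BEST diary (to day 28), and the frequency of AEs and SAEs (days 0 to 56).

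**The concern.** Leaving expected disease events out of the AE data is common and is not an error in itself. The difficulty here is an overlap: a symptom of the disease is also a form of the harm that the protocol anticipates from one of the drugs. When the exclusion is written without an exception, the same bleed may be logged as an AE by one site and passed over as disease by another, and both can say they followed section 9.2.

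The sentence justifies the exclusion by saying that the event is captured as an outcome. That is true of exacerbations. For worsening short of an exacerbation, section 3.1 has no event outcome.

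Safety counts in the trial's decisions. The Rationale says agents will be prioritised on target engagement and safety, and section 10.4 has the DMC review safety once the 10th participant in an arm reaches day 28. With 42 participants per arm bleeding events may be few, so misclassifying one or two could change the picture. The trial is open-label (section 7.4), so the choice between disease and bleed is made with knowledge of the arm and could shift the count in either direction.

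**Working it through.** This is mainly a textual check. The table follows one haemoptysis event through the rules.

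| Situation | Where the protocol puts it |
|---|---|
| Leads to admission | AE and SAE (9.2, second sentence) |
| Fatal | Reported as an SAE, even if due to disease progression (9.6) |
| No admission, part of an EMBARC exacerbation | Exacerbation outcome (3.1); not an AE, and not counted as a bleed |
| No admission, no exacerbation, attributed to bronchiectasis | Not an AE (9.2); no event outcome in 3.1; may or may not influence QoL-B, BIM or BEST |
| No admission, judged possibly drug-related | May be recorded as an AR (9.1, 9.10), but this conflicts with 9.2 if it is also seen as worsening |
| No admission, not attributed to bronchiectasis | AE under the general definition (9.1) |

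The third and fourth rows are the gap. The fourth is the sharper one, because the outcome that 9.2 relies on is not in 3.1.

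The fifth row does not close it. Section 9.1 treats events "having a reasonable suspected causal relationship to the trial medication qualify as ARs", but it describes the causal link as one between the trial medication and an AE, and section 9.3 presents AR as a classification of an AE. If 9.2 says the event is not an AE, the starting point of the AR route is in doubt, and no order of precedence is given. Usual care has no trial drug, so even a working AR route gives no control count to compare with.

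Arithmetic for context:

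- Cited bleeding rates: placebo 74/1649 = 4.5%; dipyridamole 77/1654 = 4.7%. These patients had had a stroke or transient ischaemic attack. Section 2.1 calls this trial the first use of the drugs in bronchiectasis, with possible unknown risks.
- Display threshold in section 10.3: 0.10 × 42 = 4.2, so at least 5 of 42 participants in one of the compared arms.
- The protocol gives no haemoptysis rate. Assume 2%, 5% or 10% of participants affected, with every event logged. The chance that a given arm of 42 reaches 5, from the binomial tail P(X ≥ 5), is 0.1%, 6% and 41%.
- The chance of at least one affected participant among the first 10, 1 − (1 − p)^10, is 18%, 40% and 65% at the same rates.

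These figures do not measure how many events 9.2 loses. They show that numbers could be small at the early review, and that haemoptysis could be logged correctly and still not appear in the main AE table.

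**The case against.** The strongest reply is that 9.2 never says haemoptysis is not an AE. The general definition is broad ("Any untoward medical occurrence in a participant to whom a medicinal product has been administered", related or not), and the causality scale in section 9.1 names underlying disease among competing explanations for an event graded possibly related. The protocol therefore expects disease-confounded events to be assessed. An important medical event can be serious without admission. Section 6.3.2 keeps patients on anticoagulants or dual antithrombotics, those with coagulation disorders and those with recent major haemorrhage out of the dipyridamole arm. Section 7.7 asks for an unscheduled visit for any safety concern. Section 3.1 includes symptom instruments as well as exacerbations.

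Much of this stands. A reader might infer that all worsening is kept out of the safety data, that haemoptysis appears in no data set, or that the dipyridamole arm must look safe by definition. The documents support none of these. Admissions and deaths are captured, and the rest depends on how the investigator classifies the event. Whether the EMBARC definition, QoL-B, BIM or BEST records haemoptysis cannot be settled here, because their content is not reproduced. The DMC charter is not shown either, so its reports cannot be said to lack these events.

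What the reply does not supply is a rule for the overlap. A symptom score or diary entry is not an AE record, and BEST ends at day 28 while the safety window runs to day 56. The arm-specific exclusions lower the bleeding risk but do not determine how a bleed is recorded. Appendix 1 still admits participants on aspirin, while section 8.9 lists antiplatelets as increasing bleeding risk with dipyridamole.

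**Conclusion.** The point holds for haemoptysis that does not lead to hospitalisation or death. For that event section 9.2 permits omission from the AE log, relies on an outcome that section 3.1 does not contain unless the event is an exacerbation, and leaves its relation to the AR definition open. The effect is inconsistent capture and a bleeding comparison with usual care that depends on unblinded judgement.

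The loss is possible rather than certain, and no count of lost events can be given. The conclusion rests on reading worsening of bronchiectasis as able to include a symptom that the Background itself lists for the disease. The cited bleeding rates show no excess with dipyridamole, but in a different population. The change should be made because it is cheap and concerns a risk the protocol itself names; it is not evidence that the arm is unsafe.

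**What to change.** Add to section 9.2: New or increased haemoptysis is recorded as an AE in every arm, whether or not it is attributed to bronchiectasis or occurs with an exacerbation. State that this takes precedence over the other exclusions in that section, and add a prompt to the AE log.

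In section 10.3 and in the DMC reports, list haemoptysis by arm even when it falls below the 10% threshold.

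The exacerbation outcomes stay as they are; an event may be counted both as part of an exacerbation and as a haemoptysis AE. The change affects recording only and alters no treatment. The cost is one sentence, one prompt and some additional AE entries, including mild episodes that belong to the disease. Recording them in all arms under one rule is what makes the comparison with usual care interpretable.
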